### Local Radiologist Read

A radiological read will be performed for any incidental pathology, this will ideally be done within five working days of image collection. If abnormalities are seen UCL will liaise with the recruiting site and ensure the participant's GP and/or local neurologist are informed if relevant.

The following analysis will be performed by the dedicated image analysis team at UCL:

- Whole brain, ventricular, caudate and putamen volumes and change over time (Peter A. Freeborough & Fox, 1997; Hobbs et al., 2009).
- Assessment of neurite density using Neurite Orientation and Dispersion Diffusion Imaging (NODDI) (H. Zhang et al., 2012) to detect subtle changes in microstructure which are complementary to macrostructural information provided by volumetric imaging, and change over time.
- Change in grey- and white-matter density using within-subject non-linear registration (Peter A. Freeborough & Fox, 1998) and voxel-based morphometry (VBM) (Ashburner & Friston, 2000)
- Resting state fMRI region analyses and principal component analyses. Seed connectivity will be used to identify brain regions which are simultaneously activated at rest. Dynamic causal modelling (Johnson et al., 2019) will be used to explore causal interactions between the brain and these regions. Changes in these metrics over time will be estimated.
- Brain cellular microstructure and structural connectivity will be examined using volumetric MRI combined with NODDI. Computational approaches will be applied to visualize neural tracts and to determine the relative strength of anatomical connections between brain regions. Graph theory (McColgan et al., 2015) will be used to detect changes in the organization of brain networks such as integration and efficiency. Statistical parametric mapping will be used to

HD Young Adult Study 2.0, EDGE (Sponsor) number: 145646, IRAS number: 303499, Protocol, Version 3.1, 7th Sept 2023

identify any differences in myelination within gene carriers. Change over time in these metrics will be estimated.

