## 8 DATA ANALYSIS

The HD Young Adult Study collected baseline data between April 2017 and April 2019 for 64 premanifest gene carriers and 67 healthy controls. We conducted clinical assessments, 3T imaging including volumetric, NODDI, multiparametric mapping and resting state fMRI as well as cognitive testing and blood and CSF sampling. Power calculations for the baseline sample suggested that with a type 1 error rate of 5%, a sample of 60 participants/group would provide 80% power to detect a mean difference versus controls of 0.53 adjusted within-group standard deviations (effect size), allowing for 5 covariates. Similarly, after allowing for 5 covariates, the sample of 60 CAG-expanded participants allows the same statistical power for detecting a partial Pearson correlation of 0.36 among outcome measures and between these measures and the CAG-length Age Product (CAP) score or other potential predictors of HD risk. We found significant volume reduction in the putamen in the absence of any other differences in brain macro- or microstructure, connectivity or function (Scahill et al., 2020) . Cognition was intact but there were elevated levels of Neurofilament light protein (NfL) suggestive of neuronal injury. We suggest this provides an optimum time window to administer treatments prior to widespread neuronal damage in order to delay or prevent the onset of symptoms.

In order to understand whether the putaminal volume reduction present in the premanifest gene carriers is neurodevelopmental or neurodegenerative it is necessary to obtain longitudinal data to establish whether there is ongoing atrophy. Longitudinal data will also provide information on the stability of other brain measures and identify a time at which they start to deviate from the normal range. We anticipate that after this time interval of ~5 years those participants with the highest disease burden i.e. those who are closer to expected disease onset may start to show subtle early signs of structural loss, breakdown in connectivity and cognitive deficits. This time interval was selected following power calculations by our statistician [name] of the University of Iowa who determined that this would provide 80% power to detect mean case-control differences in change over time.

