measurements collected in HD-YAS 2.0. Unless otherwise noted, outcomes are continuous or pseudo-continuous measures. By default, we will use general least-square linear models to evaluate possible overall group differences and age interactions between the young adult premanifest HD gene carriers and controls. Within these same models, we will control and test possible CAG-length-driven differences within premanifest HD gene carriers. Covariates will include age, gender, site and age interactions with gender. The main hypothesis of group differences will be evaluated by least-square means.

The primary cross-sectional analyses model will have a nearly identical generic form to that used in the original baseline analysis:

$$y = b_0 + I_{pHD} * (b_1 + b_2 * CAG + b_3 * age + b_4 * CAG * age) + b_5 * age + b_6 * sex + b_7 * age * sex + b_8 * NART + b_9 * EducLevel + r_{subject} + e$$

where y is an outcome variable, $I_{pHD} = 1$ if a participant is from the premanifest HD gene carrier group and 0 otherwise, the b 's are linear regression coefficients, $r_{subject}$ is a subject-specific random effect applicable to participants who have had two measurements, and e is the residual random error term. Both $r_{subject}$ and e are assumed to be independently, identically normally distributed among the participants with 0 mean. (See above for contingencies when these distributional assumptions prove empirically untenable.) Note that NART score (a proxy for estimated baseline IQ) and education level will only be used for cognitive outcomes.

Hypothesis 2: There is evidence of disease-related *longitudinal* change ~20 years from expected symptom onset in: a) brain imaging; b) cognition; c) neuropsychiatric function; and d) biofluid measures.

The longitudinal analyses will build on the above model by adding these further regression terms:

$$a_0 * follow-up + I_{pHD} * follow-up * (a_1 + a_2 * CAG + a_3 * age + a_4 * CAG * age) + follow-up * (a_5 * age + a_6 * sex + a_7 * age * sex + a_8 * IQ,)$$

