Neuroimaging	
Regional brain volume
 
 • Whole brain (cross-sectional volume and change YAS 1-2) • Putamen (plus HD-ISS classification) • Caudate (cross-sectional volume and change YAS 1-2) (plus HD-ISS classification) • Ventricles (cross-sectional volume and change YAS 1-2) • Grey matter (cross-sectional volume and change YAS 1-2) • White matter (cross-sectional volume and change YAS 1-2) 
Structural brain connectivity
 
 • 6 cortico-striatal connectome • 14 corticocortical connectome 
NODDI
 
 • Fractional Anisotropy • Mean Diffusivity • Radial Diffusivity • Orientation Dispersion Index • Neurite Density Index 
MPM
 
 • R1(iron & myelin) • R2* (iron/oligos) • MT (myelin)
Cognitive/emotional function	
Cognitive Flexibility
 
 • IED ED Shift Errors • IED Failures at Stage 8 
Processing Speed
 
 • SDMT (total correct) (plus HD-ISS classification) 
Verbal Fluency
 
 • Animals (total correct) 
Interference
 
 • Stroop Interference (total correct) 
Inhibition
 
 • Stop Signal Reaction Time 
Emotion Cognition
 
 • Intensity Morphing Decreasing (Negative Emotions only) • Moral Emotions Agent Guilt Score 
Planning
 
 • OTS Minimum Move solutions

	
Learning
 
 • IED pre-ED Errors • IED ED reversal errors 
Attention
 
 • RVP A' • RVP Mean Latency (for correct trials) 
Memory
 
 • PAL Total Errors Adj • SWM between errors 
Motivation
 
 • Goals Prior Assay Task Slope

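### The Hypothesis 1 model for cross-sectional brain volumes has no head-size term, and neither document says volumes are scaled for head size, so avoidable between-person variance stays in those contrasts.

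*SAP*

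**What the plan says.** Under Hypothesis 1, the SAP introduces the cross-sectional model with the sentence "Covariates will include age, gender, site and age interactions with gender". The equation below it contains carrier status; CAG length, age and their product within carriers; age, sex and age by sex; NART; education; and a subject random effect for people measured twice. Site is in the sentence but not in the equation. The SAP adds that NART score and "education level will only be used for cognitive outcomes", so imaging outcomes get neither.

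Table 1 of the SAP lists six measures under "Regional brain volume": whole brain, putamen, caudate, ventricles, grey matter and white matter. The image-analysis list in the protocol (Local Radiologist Read) has "Whole brain, ventricular, caudate and putamen volumes and change over time". Neither list describes a volume as normalised. Protocol section 8 names age, gender, IQ and CAG terms as covariates. Head size and intracranial volume appear nowhere in either document.

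The SAP does tailor the generic model elsewhere: for cognitive outcomes through NART and education, and for boundary-shift outcomes through a separate change-rate equation under Hypothesis 2. It makes no such provision for cross-sectional volumes.

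**The concern.** People with larger heads tend to have larger brain structures. Sex accounts for part of that and the rest goes into the unexplained variance. Head size is stable in adults, so in this model it falls into the subject random effect. A second visit does not average it out, and the added power that the SAP expects from repeat measurements does not remove it.

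Two things follow for the cross-sectional volumes. The carrier-control contrast is noisier than it need be. In addition, the groups are matched on age, gender and education but not on head size, so a chance imbalance passes into the volume contrast. Retention was 89% in carriers and 67% in controls, with 9 and 14 new recruits respectively, so any balance at baseline cannot be taken for granted now.

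Smaller striatal volume is the one structural difference that the SAP reports from baseline. Hypothesis 3 then uses only pathological measures that differ between groups under Hypotheses 1 and 2, so a volume missed for lack of precision would also drop out there.

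**Working it through.** **1. The plan's own figures.** Protocol section 8 says that, at a 5% type 1 error rate, "a sample of 60 participants/group would provide 80% power" for a difference of "0.53 adjusted within-group standard deviations (effect size), allowing for 5 covariates". Sidedness is not stated; two-sided is assumed.

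Power = 1 − F(t₀.₉₇₅; df, λ), where F is the noncentral t distribution, df = n₁ + n₂ − 2 − 5 and λ = d / √(1/n₁ + 1/n₂).

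- With 60 per group, df = 113: detectable d = 0.516, and power at 0.53 is 82.1%.
- With the variance inflated by 1 + 5/113 for overlap between covariates and group: detectable d = 0.527, and power at 0.53 is 80.4%. This rounds to the stated 0.53.
- The companion statement, "detecting a partial Pearson correlation of 0.36" with 60 carriers, comes out at 0.359.

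Both stated figures reproduce. The rest uses the simpler version without the inflation factor.

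**2. The sample that the Hypothesis 1 model uses.** The SAP describes a repeat of the HD-YAS 1.0 analyses with the HD-YAS 2.0 measurements added, and a random effect for people seen twice. Unique participants, from the SAP's Overview and Cohort sections:

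- Carriers: 64 + 9 = 73
- Controls: 67 + 14 = 81

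The number with a usable scan in the pooled set is not given, so 73/81 is an upper bound. Applying the 91% scanned at HD-YAS 2.0 to both groups (an assumption) gives 0.91 × 73 ≈ 66 and 0.91 × 81 ≈ 74.

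**3. Effect of adjustment.** Let r be the partial correlation of head size with a volume, given age and sex. The documents give no value; r = 0.3 to 0.6 is assumed. The residual SD is multiplied by √(1 − r²), one further degree of freedom is spent, and the equivalent sample-size gain is 1/(1 − r²) − 1:

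- r = 0.3: 1/0.91 − 1 = 10%
- r = 0.5: 1/0.75 − 1 = 33%
- r = 0.6: 1/0.64 − 1 = 56%

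Each person is counted once. Differences are in SDs of the model without head size. The 0.45 SD difference is illustrative.

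| | Detectable at 80% power, 73/81 | Power at 0.45 SD, 73/81 | Power at 0.45 SD, 66/74 |
|---|---|---|---|
| No head-size term | 0.455 | 79% | 75% |
| r = 0.3 | 0.434 | 83% | 79% |
| r = 0.5 | 0.394 | 89% | 86% |
| r = 0.6 | 0.364 | 93% | 91% |

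**4. Chance imbalance.** The SD of the group difference in head size, in SDs of head size given age and sex, is √(1/73 + 1/81) = 0.161. A one-SD imbalance shifts the volume contrast by r × 0.161, which is 0.05 SD at r = 0.3 and 0.10 SD at r = 0.6.

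**The case against.** **Correction may be made elsewhere.** The SAP calls the equation generic and close to the baseline model without saying what differs, its covariate sentence is not worded as exhaustive, and the protocol leaves imaging details to operating procedures. Volumes may therefore already be scaled. This stands as a possibility, and the documents do not support a claim that head size is certainly ignored. But protocol section 8 promises that all analyses will be prespecified in the SAP. If scaling is done, it belongs there.

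**The longitudinal questions matter more.** The follow-up was designed chiefly to detect ongoing atrophy. The two imaging measures among the five primary biomarkers under Hypothesis 5 are putamen volume change and caudate boundary shift. Head size largely cancels in within-person change. This stands, and it confines the point to Hypothesis 1a. A reader might infer that the study's main imaging results are compromised; the documents do not support that.

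**Power may look worse than it is.** Taking 91% of the 66 carriers and 59 controls seen at HD-YAS 2.0 gives about 60 and 54. From these a reader might infer a detectable difference of 0.530 SD and only 66% power at 0.45 SD. The Hypothesis 1 model pools both studies, so those figures do not describe it.

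**Adjustment could remove a real effect.** Protocol section 8 leaves open a neurodevelopmental explanation for the smaller putamen, and head size could be part of it. This is a good reason to report the unadjusted contrast too. It is not a reason to leave the choice unstated.

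**Conclusion.** The point holds for the cross-sectional volumes under Hypothesis 1a. It is a matter of efficiency and prespecification: chance imbalance adds noise, not systematic bias, and the protocol's power figures are correct on their own terms.

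The direction follows for any non-zero partial correlation between head size and volume. The size depends on the assumed r. At r = 0.3 the gain is modest (79% to 83% power at 0.45 SD); at r = 0.6 it is substantial (79% to 93%). The absolute figures also depend on the pooled number scanned, for which 73/81 is a ceiling, and on counting each person once. The relative gain of 10% to 56% does not depend on the sample size.

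**What to change.** In the Hypothesis 1 section of the SAP, add total intracranial volume as a covariate in every cross-sectional volume model, as one fixed value per participant from the T1 scan already acquired. Name the adjusted contrast as the one that enters the domain-level false discovery rate. Report the unadjusted contrast as a sensitivity result, since head size could itself be affected by neurodevelopment. If volumes are already scaled for head size, state this and the method in the SAP instead, with the same rule on which contrast counts. Boundary-shift models need no change for this point.

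The cost is deriving one value per participant from existing scans, one degree of freedom, and a second reported contrast for each volume. The choice should be fixed before the volume contrasts are examined.

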where the regression coefficients a. estimate the longitudinal influence of follow-up time with the covariates listed in the original cross-sectional model. One other difference between the cross-sectional and longitudinal analyses is that the cross-sectional analysis will use age at each visit as a covariate, whereas the longitudinal analysis will use age at baseline. This is because changes of age with follow-up and length of follow-up are redundant measures. A readily interpreted assessment of observed longitudinal change with follow-up requires that the age term in the model remains constant.

Boundary Shift Intervals (BSI) measures of MRI volumetric change will require a modification to the above longitudinal model, since these are a direct estimate of change between two MRI scans. Boundary shift volumes will be divided by time between the MRI scans, and the resultant statistic will be used as a volume change rate. This volume change rate will be the outcome variable, y, subjected to analysis.

$$y = b_0 + I_{pHD} * (b_1 + b_2 * CAG + b_3 * age + b_4 * CAG * age) + b_5 * age + b_6 * sex + b_7 * age * sex + b_8 * IQ + e$$

The age term in this BMI model again represents baseline age for the participants, to avoid confounding of changing age and follow-up time in the study. Since there will at most a single BMI measure per participant, the model will contain only a simple residual error term. No subject-specific random effects are estimable.

Hypothesis 3: Early pathological events lead to impairment in isolated functional domains such as cognitive flexibility.

Statistical analyses will only examine potential associations between early pathological events and functional impairment. Issues of causality will remain the subject of logical scientific conjecture. Analyses will be limited to combinations of pathological measures and functional measures that demonstrate differences between the HD gene carriers and controls, per the mixed model analyses described above to address Hypotheses 1 and 2.

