For the functional measures used, we will assess both cross-sectional and lagged associations with pathological measures using the combined data from HD-YAS 1.0 and HD-YAS 2.0. To test cross-sectional associations, we will add the contemporary pathological measures as additional potential predictors in the cross-sectional models of the form defined above for hypothesis 1. These analyses will be limited to only the HD gene carriers and will therefore not include terms for HD-carrier versus control status or interactions of that genetic status.

We will further test for a potential lag between pathological events and measurable impairment using only the cross-sectional data impairment data from HD-YAS 2.0. Analyses will be limited to those from the HD-YAS 1.0 who also participated in HD-YAS 2.0. With single HD-YAS 2.0 functional observations per participant, we will estimate ordinary least squares regression models using both the baseline and follow-up (HD-YAS 2.0) pathology measures. (Subject to potential adjustments for violation of mathematical modeling assumptions as discussed in the General Methods section above). We will test for an association between HD-YAS 1.0 pathology measures and HD-YAS 2.0 functional measures. We will further estimate the joint associations of the HD-YAS 1.0 and HD-YAS 2.0 pathology measures by including both as joint predictors of the functional outcome. We will also refit the models by re-parameterizing the 1.0 and 2.0 values as the 1.0 value and the change in the pathology measure between 1.0 and 2.0. Other covariates in these models will be the same as described for the previous analyses (age, sex, CAG length, CAG by age interaction, and in the case of cognitive functional measures, baseline NART and Education level scores).

Within the premanifest HD gene carrier group, we will determine how well the clinical and neuroimaging variables are predicted by CSF levels of mHTT and by CSF and plasma levels of NfL. Analyses will be performed one biomarker one at a time and have the general form:

$$y = b_0 + b_1 * \text{biomarker} + b_2 * \text{age} + b_3 * \text{gender} \\ + b_4 * \text{age} * \text{gender} + b_5 * \text{IQ} + r_{\text{subject}} + e$$

Additionally, we will assess evidence of longitudinal prediction of change in HD measures by adding the additional terms to the above model.

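### The pooled Hypothesis 3 and 4 association models have no visit or follow-up term, so a between-visit shift off the cross-sectional age line and present in both measures leaks into the association coefficient

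*SAP*

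**What the plan says.** Under Hypothesis 3 the SAP combines both visits: "we will assess both cross-sectional and lagged associations with pathological measures using the combined data from HD-YAS 1.0 and HD-YAS 2.0". For the contemporary associations, "we will add the contemporary pathological measures as additional potential predictors in the cross-sectional models of the form defined above for hypothesis 1", in carriers only. The Hypothesis 1 equation has age, sex, CAG and CAG-by-age terms and a subject effect that "is a subject-specific random effect applicable to participants who have had two measurements". It has no visit or follow-up term. The text under Hypothesis 2 explains the time scale: "the cross-sectional analysis will use age at each visit as a covariate, whereas the longitudinal analysis will use age at baseline", because "changes of age with follow-up and length of follow-up are redundant measures".

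Hypothesis 3 then gives a second model for CSF mHTT and for CSF and plasma NfL: "Analyses will be performed one biomarker one at a time and have the general form". That equation contains the biomarker, age, gender, their interaction, IQ and a subject effect. It has no CAG term and no follow-up term, and it does not say which age is meant. Hypothesis 4 applies the same models to somatic expansion.

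Two neighbouring analyses differ. The longitudinal extension, where "we will assess evidence of longitudinal prediction of change in HD measures by adding the additional terms to the above model", includes a follow-up main effect and separate baseline and change terms for the biomarker. The lagged models use one HD-YAS 2.0 outcome per participant.

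**The concern.** In the two pooled base models age is the only variable that moves with time. A carrier seen twice contributes a within-person change, while carriers of different ages contribute a between-person gradient, and one coefficient has to fit both. The two can differ when there are practice effects, assay batch differences, or progression that does not follow the cross-sectional gradient. Change that age does not absorb stays in both predictor and outcome. If both carry some, the association coefficient b1 picks it up even when the measures are unrelated across people.

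At stake is the reading of b1. Hypothesis 4 asks whether people with more somatic expansion have more pathology. The pooled coefficient mixes that with whether both measures moved over 4.5 years. Shifts in opposite senses can also mislead: a practice gain alongside rising NfL would push b1 towards better cognition at higher NfL.

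**Working it through.** **Inputs from the documents.** There are 57 carriers with two visits, 64 − 57 = 7 with the first visit only, and 9 new carriers with the second only (SAP, Overview and The Cohort). The gap is about 4.5 years.

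**Assumptions.** Baseline age is uniform on 18–40, so its variance is V = 22²/12 = 40.3. The correlation between visits is ρ = 0.8 or 0.9. The shift is 0.2, 0.3 or 0.5 SD in both measures, with no between-person age slope and no true association.

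**The plan's own figure.** None is given for these models. The nearest is 80% power for a partial correlation of 0.36 with 60 carriers and 5 covariates (protocol section 8). The noncentrality is 0.36/√(1 − 0.36²) × √55 = 2.862 and the two-sided critical t on 53 df is 2.006, giving 80.2%. It reproduces, but it concerns single-visit data and does not test this point.

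**How much of the shift age absorbs.** With total variance 1, the information on the age slope is:

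- within person: W = 57 × 4.5²/2 ÷ (1 − ρ)
- between two-visit carriers: B = 2 × 57 × V ÷ (1 + ρ)
- from single-visit carriers: S = 16 × V

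For ρ = 0.8, W = 2,886, B = 2,554 and S = 645, so the within-person share W/(W + B + S) is 0.47. For ρ = 0.9 the values are 5,771, 2,420 and 645, and the share is 0.65. Age at visit thus removes only about half to two-thirds of an off-line shift.

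**What leaks.** Let Δx and Δy be the gaps between the within-person and between-person yearly slopes of predictor and outcome. The leaked cross-product is approximately C = Δx Δy × W(B + S)/(W + B + S). It is zero if either gap is zero. For equal gaps, b1 ≈ C/(130 + C) with standard error ≈ 1/√(130 + C), where 130 = 2 × 57 + 16 observations.

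For a 0.5 SD shift, Δ = 0.5/4.5 = 0.111 per year.

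- ρ = 0.8: C = 0.0123 × 1,517 = 18.7, so b1 ≈ 18.7/148.7 = 0.126 (SE 0.082)
- ρ = 0.9: C = 0.0123 × 2,002 = 24.7, so b1 ≈ 24.7/154.7 = 0.160 (SE 0.080)

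**Simulation.** Random-intercept REML, 1,000 runs per setting. Monte Carlo error is about 0.7 points at 5% and up to 1.6 points near 50%. Each cell gives ρ = 0.8 / 0.9.

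| Shift in both | b1, formula | b1, simulated | Rejects, age at visit | Rejects, baseline age only | Age at visit + visit indicator | Baseline age + follow-up |
|---|---|---|---|---|---|---|
| 0.2 SD | 0.023 / 0.030 | 0.020 / 0.028 | 5.9 / 6.5% | 8.5 / 13.4% | 5.3 / 5.0% | 5.5 / 6.0% |
| 0.3 SD | 0.049 / 0.064 | 0.049 / 0.064 | 8.5 / 11.1% | 15.2 / 38.1% | 5.3 / 5.0% | 5.9 / 5.9% |
| 0.5 SD | 0.126 / 0.160 | 0.130 / 0.164 | 29.5 / 44.9% | 59.0 / 92.9% | 5.3 / 5.0% | 6.0 / 6.2% |

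Drift that follows the age line (0.03 SD a year in both measures, opposite directions) gives 5.6 / 4.7% with age at visit. A 0.5 SD shift in one measure only gives 5.2–6.5% (ρ = 0.8, 400 runs).

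**Sensitivity to the age gradient.** A separate simulation with visit correlations of 0.90 and 0.95 gave 7, 10, 20 and 31% at 0.2, 0.3, 0.4 and 0.5 SD with no between-person age slope. It gave 5, 6 and 9% at 0.2, 0.3 and 0.4 SD when the between-person slope was half the within-person slope. That fits the formula, since halving both gaps quarters C. Equal slopes gave near-nominal error.

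**CAG-dependent progression.** In another simulation (800 runs) two unrelated measures both progressed with age times excess CAG length under a disease-burden cap of 240. The burden formula is an assumption, as the documents do not give it. Rejection at 0.2, 0.3, 0.4 and 0.5 SD was:

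- Hypothesis 1 form, no follow-up term: 6.0, 6.4, 3.8 and 5.2%
- Hypothesis 1 form, baseline age plus a follow-up main effect only: 6.1, 6.4, 7.2 and 10.4%
- biomarker form, no follow-up term: 10, 28, 60 and 88%
- biomarker form, baseline age plus follow-up: 8, 19, 42 and 71%

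Most of the excess in the biomarker form comes from the missing CAG terms.

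**The case against.** The strongest reply is that the SAP already has a time variable in the cross-sectional form, age at each visit, and says why it does not carry follow-up as well. This stands in part. A reader might infer that any drift common to everyone is read as an association. The documents do not support that: drift along the age line is absorbed, and both measures must be off it. The redundancy remark does not settle the rest. Change in age equals follow-up within a person, but baseline age and follow-up are distinct, and Hypothesis 2 uses both.

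A reader might also infer that the disease-burden limit makes the between-person age slope understate progression and so biases the Hypothesis 1 form. That does not hold. I read the carriers-only model as keeping CAG and CAG-by-age, since the lagged models list them among the covariates carried over, and with them error stays at about 4 to 6%. Scanner shift is a weak example too, because the protocol (Imaging assessment) keeps the baseline 3T scanner.

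Three further points have some force. Hypothesis 3 admits only measures that differ between carriers and controls, so practice or batch drift shared by both groups does not by itself qualify a pair. However, Hypothesis 2 selects on differential change, so measures that move in carriers can qualify. The SAP Overview reports higher NfL nearer to expected onset, which argues against a zero between-person gradient and so against the largest figures for NfL. Finally, shared within-person worsening may be the association that some readers want. That is a choice of estimand, and a reason to report between-person and within-person parts separately.

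**Conclusion.** The concern holds in a limited form. Both pooled base models, and their reuse for Hypothesis 4, lack a visit or follow-up term, and an off-line shift in both measures biases b1. The inflation of a 5% test is slight at 0.2 SD (about 6 to 7%), moderate at 0.3 SD (8 to 12%) and serious at 0.5 SD (of the order of 25 to 45%; 29.5 and 44.9% in the table). These sizes rest on assumed shifts, visit correlations and age spread. The documents give no drift or practice effect, so the figures are illustrative. If age in the biomarker equation means baseline age, the problem is much larger (8.5 to 92.9% over the same settings), which is reason enough to settle the wording.

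Two wider readings should be avoided. The sentence on combined data also mentions lagged associations, but the lagged least-squares models have one outcome per person and are not affected. Nor is the longitudinal extension, which has a follow-up main effect. And a follow-up term does not repair everything: in the biomarker form, confounding by CAG-dependent progression remains until CAG terms are added.

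**What to change.** In every pooled Hypothesis 3 and 4 base model, either add a visit indicator and keep age at visit, or use baseline age plus follow-up as in Hypothesis 2. If the second route is taken, carry over the Hypothesis 2 follow-up interactions with CAG and age as well, since a follow-up main effect alone reached 10.4% in the CAG-dependent case.

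State which age the biomarker equation uses, and add CAG and CAG-by-age to it, as in the Hypothesis 1 form. Preferably also split the predictor into its baseline value and its change from baseline and report the two coefficients separately. The SAP already does this in the lagged models and the longitudinal extension.

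The cost is one or two extra terms per model, plus the two CAG terms in the biomarker form, and a slightly wider interval for b1. No new data are needed.
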